Aim 2 Analysis. The goal of Aim 2 is to determine whether the intervention satisfactorily impacts the hypothesized theoretical mechanisms. As an exploratory outcome, we will also assess PA. Participant ratings of meaning salience (average of 3 measures across the week), basic psychological needs satisfaction, and internal motivation will each be compared across four time points (weeks -4, 0, 4, 8) using multilevel linear modeling with time points nested within participants to control for repeated measures variance. A fixed time effect will estimate participant ratings at each time point relative to baseline, and a series of linear contrasts will test our hypotheses about the pattern of change in ratings over time. Without intervention, we do not expect to see change in hypothesized mechanisms so that a week -4 vs. week 0 contrast will be close to zero. Following intervention implementation, however, we expect participants to report increases in the theoretical mechanisms so that contrasts comparing weeks 4 and 8 to baseline will each be positive. Furthermore, we expect to see the greatest change in the first 4 weeks post-intervention so that a week 8 vs. week 4 contrast will be close to zero.

Exploratory Aim Analysis. In exploratory analyses, we will use this same approach as Aim 2 to examine changes in PA and whether the hypothesized mechanisms are related to PA over time (i.e., pre-intervention, early intervention, and late intervention stages). First, we will examine whether the difference in PA slope during the active intervention phase (week 0 to week 8) is significantly greater than the change observed during the pre-intervention phase. Additionally, we will examine whether changes in hypothesized mechanisms (meaning salience, needs satisfaction, and internal motivation) from week 0 to week 4 are associated with changes in PA from week 0 to week 8 using growth curve modeling. Although this pilot study will not be powered to determine statistical significance, the effect sizes will be calculated to assess the extent to which the intervention is impacting the hypothesized mechanisms.

g. Power analysis

Aim 2 Power. In this pilot, the aim is not to determine statistical significance but rather to assess whether MAP to Health is likely to increase the hypothesized mediators enough to elicit meaningful change in PA (Cohen's $d \geq 0.30$). Based on our previous observational study,⁵² the strength of the observed relationships in Figure 1 are expected to be $\beta = .55$ (needs satisfaction to internal motivation), $\beta = .30$ (internal motivation to PA), $\beta = .16$ (needs satisfaction to meaning salience), and $\beta = .10$ (meaning salience to PA). Therefore, if half of the total intervention effect ($d = .30/2 = .15$) is mediated through the pathways in Figure 1, then the intervention will need to increase both needs satisfaction (estimated $\beta = .50$) and meaning salience (estimated $\beta = .60$) by $d > 0.55$. The remaining $d \approx 0.15$ of the total effect would be represented as a direct effect on PA and could be obtained at least in part via unmeasured mediators. If the week -4 vs. week 0 comparison yields a difference of approximately 0, the week 4 vs. week 0 comparison is similar in power to a paired t -test. A paired t -test with a sample size of $N = 35$ is powered (0.80, $\alpha = 0.05$) to detect differences of $d \geq 0.49$. As such, the planned analyses may be sufficiently powered to detect meaningful within-person changes in the hypothesized mediators.

h. Strengths and Limitations

This study has several strengths, including building off a previously developed prototype intervention that used a psychometric approach to intervention development (COMAP), using a systematic approach to developing and testing the intervention (using the ORBIT and SOBC models), and building off a solid base of observational and interventional research based on SDT and meaning. Further, we have a strong interdisciplinary team with the resources to carry out the proposed work.

The study is designed as a proof-of-concept pilot trial. Participants will serve as their own controls instead of being compared to a no-intervention control group and our sample size is small. These design choices were made to ensure the intervention was related to changes in the hypothesized

mechanisms; however, we will be limited in our abilities to state that the intervention was related to changes in physical activity.

There are two potential biases that we will be sure to address during the project. First, in longitudinal studies, there is always data loss due to participants not completing assessments. To reduce data loss, we will use multiple reminders to encourage participants to complete follow-up assessments (up to 3 reminders per assessment). Further, we will provide compensation for participants to complete each of the assessments to encourage continued participation. Finally, multilevel modeling allows for use of all available data, so participants will not be completely dropped from analysis if they miss any of the assessments.

Second, objectively measured PA using accelerometers has the advantage over self-report PA in reducing measurement bias.⁷⁴ However, it also requires that participants wear the devices and can be subject to data loss due to hardware malfunction. Participants will be encouraged to wear devices on their wrist during daytime hours and data will be uploaded to a cloud-based data management system. Research staff will call participants and remind them to wear or charge the device if needed.

6. Setting/Environment/Organizational feasibility

This study will be conducted at HealthPartners Institute (HPI). HPI is a particularly appropriate setting because we have the research infrastructure and staffing capacity to build the MAP to Health intervention (SET team), serve hundreds of thousands of midlife adults who may benefit from this intervention in care group and health plans, and have experience designing and evaluating technological innovations. During the development of this proposal, we sought the support of the health plan's Health Promotion department ([name], leader) in the potential of integrating MAP to Health in the Be Well offerings should it be funded. We will continue to engage the Health Promotion team to ensure we are developing an intervention that will fit with their product offerings.

7. Risks and Benefits

a. Potential Risks

In terms of procedures, measurements, and data collection methods, this is a low risk study. Many adults attempt to start physical activity programs on their own every year; this study would not impose a specific plan or program for activity but would rather capitalize on participants' motivation to change and encourage free choice of activities. As with any physical activity, there is a slight risk that participants could get injured during the study. A second risk is the risk of loss of confidentiality. HealthPartners Institute has procedures to ensure that confidentiality will always be protected and that potential risks are systematically minimized.

b. Potential Benefits

There are no direct benefits to participating in this research study to the participant. As a result of participating in the proof-of-concept trial, some participants may increase physical activity, which has been shown to have many health benefits. The major benefit of this study is the knowledge gained about how the intervention impacts the hypothesized mechanisms of behavior change and physical activity.

c. Protection Against Risks

To reduce risks of injuries as a result of engaging in physical activity, we will encourage participants to engage in activities that are consistent with their current levels of physical fitness and to rest when needed.

To reduce the risk of breach of confidentiality, we will access and employ only the minimally necessary EHR data to identify and screen potentially eligible participants and to contact them for recruitment. We will maintain the confidentiality of all study data by assigning an arbitrary and unique subject identification number to each participant. We will maintain study data on computerized databases on username- and password-protected file servers at HPI to which only staff and researchers involved in the study will have access. No participant data will be individually identified or released to anyone other than the study investigators without specific written permission from the study participant. All procedures will be reviewed in advance, approved, and monitored on an ongoing basis by the HealthPartners IRB.

8. Data Confidentiality and Privacy

The study team has extensive experience in health services research and clinical research with human subjects, with procedures to safeguard privacy and personal information. Data will be retained in secure storage following the completion of the study in accordance with Minnesota and federal law. We guard against the potential for breach of subject confidentiality through a multi-layered system of data protection policies, processes, staff training, software safeguards and physical security measures for both paper and electronic data involved in research.

The following measures will be taken to protect subjects from the risk of breach of confidentiality:

1. All data collected in the study will be identified by using an arbitrary and unique study ID number to each patient.
2. A file containing a link between the study ID and individually identifying information will be maintained by a study team programmer.
3. A crosswalk table linking the study ID to a patient identity will be destroyed within 6 months after the linked databases needed to complete study analyses are completed.
4. All electronic study data will be maintained in a computerized database residing on a username- and password-protected fileserver to which only the study team members will have access.
5. All study-related paper documents containing individually identifiable information will be maintained in locked file cabinets.

To protect the confidentiality of any clinic or organization employee participating in a survey, we will not allow anyone outside of the research team to know the identity of those respondents. All of the protection to electronic data sources, described above, also apply to survey collection.

9. Timeline: Key Milestones

Phase 1: Development
Oct – Dec 2021: Intervention Development
Finalize MAP to Health online assessment Develop text messages Develop outcome surveys Determine process for ActiGraph delivery & set up and monitoring
Oct 2021 – Jan 2022: Programming
Programming for MAP to Health online assessment Build REDCap survey for usability testing Build CESR Recruitment REDCap Develop modality for sending surveys
Feb – Apr 2022: Recruitment & Usability testing

Phase 2: Proof-of-Concept Trial
Feb – Apr 2022: Intervention Modifications
Revise text messages Revise MAP to Health online assessment Revise survey measures
Feb – Jun 2022: Programming
Updates and modifications
Jun – Nov 2022: Intervention Delivery
Recruitment (rolling) Participant Outreach (start up and reminders)

Survey Data Collection ActiGraph data collection (using CentrePoint cloud-based software)
--

Analysis & Dissemination

Dec 2022 – May 2023
Data preparation & cleaning
Data analysis
Manuscript preparation

10. Dissemination/Sharing Results/Integration and Impact

A. Reporting on ClinicalTrials.gov

Upon funding, we will register our study protocol with ClinicalTrials.gov in accordance with NIH policy no later than 21 calendar days after enrollment of the first participant. We will enter study results no later than one year after the trial's primary completion date. All participant consent forms will include specific language indicating that the study information will be registered with ClinicalTrials.gov, including the final results. The HealthPartners Institute, as part of internal policy and in compliance with federal regulations, registers all of its clinical trials on ClinicalTrials.gov.

B. Disseminating and implementing the results of this research in other settings

Regular physical activity is a key behavior for healthy aging and wellbeing. In the Healthy People 2030 goals, physical activity was named a leading health indicator, and increasing the proportion of adults who are engaging in physical activity is a core objective. Despite significant efforts to increase the proportion of physically active adults, the high rates of insufficient physical activity have not improved. MAP to Health is a resource-sparing, theory-based intervention for encouraging regular physical activity. The intervention harnesses a person's personal sense of meaning in life to increase internal motivation to engage in regular physical activity, with the goal of increasing the likelihood that physical activity will become a part of that person's regular routine. The proposed study will further develop and provide proof-of-concept testing for the intervention; if successful, we will seek additional funding for a Phase III efficacy trial to compare MAP to Health to a physical activity reminder intervention.

To ensure that the intervention can be easily disseminated within our system, we will work closely with the HealthPartners Health Promotion department, who maintains and offers several digital health promotion products to HealthPartners insurance members. We will meet with their development team prior to, during, and after intervention development to make sure the product we develop could be integrated within their health promotion package.

Because MAP to Health is an entirely digital product, it has the potential to be widely disseminated and offered to individuals across the country. There is no staffing requirement beyond regular maintenance of the digital tools. We will be open to discussing implementation of the intervention in other health systems and health plans as part of their health promotion packages. We posit that taking a systematic approach to behavioral intervention development will increase the probability of intervention success and will facilitate the likelihood that the final product will be useful to adults attempting to increase their physical activity.

Beyond these considerations, we will also promote dissemination by communicating results of this study in many ways, including through publications in peer-reviewed professional journals, communications in lay and professional media, and presentations to patients, clinicians, and health care leaders. In addition, we are willing to engage in any dissemination activities that may be suggested by the funding agency during or after the project period.

Our preliminary communication strategy for dissemination includes the following components:

- Communicate findings internally to leaders of the HealthPartners medical group and HealthPartners insurance plan
- Communicate findings to other health systems that collaborate with HealthPartners on research and care improvement initiatives (e.g., Health Care Systems Research Network)

- Publish study methods and results in peer-reviewed journals
- Present findings at scientific and professional meetings

The research team will evaluate the success of the dissemination plan iteratively in a long-term partnership with NIH, end users, dissemination partners, and stakeholders.

C. Disseminating study results to study participants after completion of analyses

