To identify potential participants, we will use electronic health records (EHRs) of patients from HealthPartners, Park Nicollet, and Stillwater Medical Group clinics who meet eligibility criteria. Then the Programmer Analyst will randomly select potential participants to recruit and screen. Recruitment samples will be stratified on sex and race/ethnicity; specifically, we will oversample racial and ethnic minorities to ensure adequate representation.

Because some eligibility criteria are not available in EHR, potential participants will be further assessed for eligibility during the phone screening process. Estimating a 2-3% participation rate, we will pull a recruitment sample of 2250 patients: 250 in Phase 1 and 2,000 in Phase 2.

For Phase 1, we will recruit up to 20 participants for usability testing. We anticipate that we will recruit a minimum of 12 participants, with three rounds of 4 participants. This sample size was chosen because it is the industry standard for this type of usability testing (~10 participants). We have included an additional 8 participants in case we need to conduct additional rounds of usability testing.

For Phase 2, we will recruit up to 45 participants for the proof-of-concept pilot trial. Our power analysis indicates that a minimum of 35 participants is needed to detect a meaningful change in the hypothesized mediators (see Phase 1 Power Analysis for details).

c. Data collection process

i. Identifying Participants

Potential participants will be identified EHRs by a Research Informatics Programmer Analyst. The Programmer Analyst will use available inclusion/exclusion criteria above to identify potentially eligible patients, stratify on sex and race/ethnicity, apply a random selection algorithm to that list, and check the research opt-out list. Once the list of potentially eligible participants has been narrowed to the appropriate sample size, the analyst will then pull demographics and contact information.

For Phase 1, we may also offer the study to employees of HealthPartners who believe they meet the study inclusion exclusion/criteria.

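### Aim 2 asks whether the mechanisms rise enough, but section 4.f never compares its effect sizes with the rise that section 4.g requires, and the power statement is not supported for internal motivation

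*Combined protocol and SAP*

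**What the plan says.** Section 4.f (Aim 2 Analysis) sets the goal: to "determine whether the intervention satisfactorily impacts the hypothesized theoretical mechanisms". Each mechanism is modelled over weeks -4, 0, 4 and 8. The expectations are about sign: no change before the intervention, then "contrasts comparing weeks 4 and 8 to baseline will each be positive", then little further change from week 4 to week 8. The last sentence of the Exploratory Aim Analysis adds that effect sizes will be calculated to gauge the impact on the mechanisms. It names no reference value and no interval.

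Section 4.g (Aim 2 Power) says that significance is not the aim. The aim is to learn whether the intervention is "likely to increase the hypothesized mediators enough to elicit meaningful change in PA", with meaningful change in PA set at d of at least 0.30. Half of that (0.15) is assumed to be mediated. From four path coefficients the section concludes that needs satisfaction (.50) and meaning salience (.60) must rise by d > 0.55. It gives no required rise for internal motivation, which section 4.e.iv lists as a primary outcome for Aim 2.

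The same section says that a paired t-test with 35 participants "is powered (0.80, $\alpha = 0.05$) to detect differences of" d of 0.49 or more, and concludes that "the planned analyses may be sufficiently powered to detect meaningful within-person changes in the hypothesized mediators".

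**The concern.** The stated question is one of magnitude, but the planned contrasts have zero as their reference. The required rises are worked out in section 4.g and not carried into section 4.f. Aim 1 has a numeric threshold (a mean of at least 4 on a 5-point scale), whereas the word satisfactorily in the Aim 2 goal has no criterion. Without one, readers are likely to fall back on whether the contrasts are significantly positive. That can happen at a rise which the plan's own model says is too small.

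Internal motivation has the opposite problem. The rise that the plan's model implies for it is smaller than the design can reliably detect. A non-significant contrast could then be read as no change even if the intervention did what the model requires. Section 10.B makes seeking funds for an efficacy trial depend on this study being successful, so both misreadings bear on a real decision.

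**Working it through.** **Inputs.** All from section 4.g unless noted: N = 35, power 0.80, alpha 0.05 (sidedness not stated); paths 0.55 (needs to motivation), 0.30 (motivation to PA), 0.16 (needs to salience) and 0.10 (salience to PA); mediated effect 0.15. Section 4.b.ii allows recruitment of up to 45.

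**1. The plan's detectable difference.** Exact paired t-test, two-sided, 34 degrees of freedom, noncentrality d√35. The detectable d at 80% power is 0.487, and power at 0.49 is 80.4%. The stated 0.49 reproduces.

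**2. The plan's required rises.**
- Needs through motivation: 0.50 × 0.55 × 0.30 = 0.0825
- Needs through salience: 0.50 × 0.16 × 0.10 = 0.0080
- Salience directly: 0.60 × 0.10 = 0.0600
- Sum: 0.1505, matching the stated 0.15

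So .50 and .60 are the values that deliver the target. The summary of d > 0.55 for both does not agree with .50 for needs. Equal rises that give 0.15 would be 0.15 / (0.165 + 0.016 + 0.10) = 0.534.

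**3. What a just-significant contrast delivers.** The smallest significant observed d is t(0.975, 34)/√35 = 2.032/5.916 = 0.344. In both mediators this carries 0.344 × (0.181 + 0.10) = 0.097, and 0.097/0.15 is about 64%. The 95% CI for an observed d of 0.344 is about 0.00 to 0.68, so such a result neither shows the required rise nor rules it out. Other settings widen the gap: a one-sided test has a cut-off of 0.286 (54%), and N = 45 has a cut-off of 0.300 (56%).

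**4. Internal motivation.** The implied rise is 0.50 × 0.55 = 0.275, or 0.55 × 0.55 = 0.3025 if needs rise by 0.55. Two-sided power with d taken as a paired d:

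| True d | N = 35 | N = 45 |
|---|---|---|
| 0.275 | 35% | 44% |
| 0.3025 | 41% | 51% |
| 0.50 | 82% | 91% |
| 0.60 | 93% | 98% |

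**5. Scale of d.** If the required rises are in raw-score SD units, the paired value is d/√(2(1 − r)), where r is the pre-post correlation. The documents do not give r; I assume 0.3 to 0.85. At N = 35:

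| r | Power at 0.275 | Significance cut-off in raw d |
|---|---|---|
| 0.3 | 27% | 0.41 |
| 0.5 | 35% | 0.34 |
| 0.7 | 53% | 0.27 |
| 0.8 | 71% | 0.22 |
| 0.85 | 82% | 0.19 |

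The cut-off stays below 0.50 throughout, so step 3 does not depend on r. Power for internal motivation does: 80% needs r of about 0.84 at d = 0.275, or about 0.81 at d = 0.3025.

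**The case against.** A reader might infer that the plan contains a significance rule that is too lenient for needs and salience and too strict for internal motivation. It does not. Nowhere does it say that p < 0.05 decides Aim 2 or that a non-significant contrast means no change. Section 4.g disclaims significance as the aim, section 4.f plans effect sizes, and H2 in section 2 predicts only increases, which a contrast against zero does test. All of this stands. What remains is that the planned effect sizes have nothing to be judged against, although section 4.g supplies the reference.

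On internal motivation, the strongest objection is that 0.275 is derived here and not stated, and that it runs through needs satisfaction alone. Section 4.d.i suggests that addressing meaning may also internalise motivation, and the model figures are not shown, so the full path diagram cannot be checked. This is fair, and 0.275 should not be called a target of the plan. It is not very sensitive to the route, however. With salience up by 0.60, the listed paths into PA leave (0.15 − 0.60 × 0.10)/0.30 = 0.30 for motivation, however that rise comes about.

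The power sentence is also hedged with the word may, and the 35% figure rests on the paired-d scale. So a reader should not conclude that the sentence is false, only that the plan's own figures do not support it for this outcome.

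**Conclusion.** The point holds in two parts.

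First, section 4.f does not connect its contrasts or effect sizes to the rise that section 4.g requires. A contrast that is just significantly positive (d about 0.34 with 35 pairs) carries about 64% of the required mediated effect, so it does not answer the question of size. This is robust to sidedness, to N up to 45 and to the assumed range of r. It is a missing benchmark, not a faulty written rule.

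Second, the power statement is not supported for internal motivation. The model-implied rise of 0.275 to 0.30 is below the detectable 0.49. Power is 35–41% at N = 35 and 44–51% at N = 45 on the plan's paired-d convention, two-sided. On a raw-score scale it is 27% to 82% at d = 0.275 and N = 35, for r from 0.3 to 0.85. This part rests on the section 4.g coefficients and on the scale of d, which the plan should state.

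**What to change.** **Section 4.f.**
- Report each week 4 versus week 0 contrast as d with a 95% CI, and state which SD is the divisor.
- Interpret it against the rise required in section 4.g, after reconciling .50 and .60 with d > 0.55.
- Describe a positive contrast that falls short as an increase, but not shown to be as large as required.
- Do not add a pass/fail bar. A point-estimate bar is met only about 51% of the time when the true rise equals the requirement. Requiring the lower 95% limit to clear 0.50 or 0.60 would need an observed d of about 0.90 or 1.01 with 35 participants.
- For internal motivation, use 0.275 to 0.30 as a model-implied reference value and judge it by estimate and CI, so that a non-significant result is not read as no change.

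**Section 4.g.** Limit the 80% power statement to needs satisfaction and meaning salience. Give the lower power for internal motivation with its assumptions: N, two-sided alpha, the scale of d and, if raw-score units are used, the pre-post correlation. The statement for needs and salience also rests on the paired-d scale: at r = 0.3 in raw units, power at 0.50 would be 68%.

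**Cost.** Wording only, with no new data or participants. The price is a less favourable power statement and a more cautious conclusion for needs and salience.

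### The early-change hypothesis rests on a week 8 vs week 4 contrast being near zero, which does not compare early with late change, has no criterion, and at N = 35 cannot by itself establish a plateau

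*Combined protocol and SAP*

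**What the plan says.** Section 4.f (Statistical Analysis Plan, Aim 2 Analysis) compares each mechanism across weeks -4, 0, 4 and 8 "using multilevel linear modeling with time points nested within participants to control for repeated measures variance". It then says that "a series of linear contrasts will test our hypotheses about the pattern of change in ratings over time". After the intervention starts, it expects that "contrasts comparing weeks 4 and 8 to baseline will each be positive", and it expects the "greatest change in the first 4 weeks post-intervention so that a week 8 vs. week 4 contrast will be close to zero". It gives no margin, interval rule or equivalence bound for the last of these, and it lists no contrast of early change against late change.

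Section 4.g (Power analysis, Aim 2 Power) treats one comparison only: "the week 4 vs. week 0 comparison is similar in power to a paired t -test". With 35 participants, power 0.80 and alpha 0.05, it gives a detectable difference of d = 0.49. It sets a target increase above d = 0.55 for needs satisfaction and meaning salience, but does not say by which week. It makes no power statement for week 8 vs week 4. It also says that "the aim is not to determine statistical significance but rather to assess whether MAP to Health is likely to increase the hypothesized mediators".

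**The concern.** The hypothesis says that the gain from week 0 to week 4 exceeds the gain from week 4 to week 8. A week 8 vs week 4 contrast looks only at the second gain. A value near zero fits the hypothesis, but so does a modest further gain that a small sample cannot see. The week 4 score also enters both contrasts with opposite sign: a chance-high week 4 raises the early gain and lowers the late one, which by itself looks like an early peak.

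At stake is a statement about the shape of response in the three primary Aim 2 outcomes (Section 4.e.iv), namely whether the mechanisms keep rising in the second half of an 8-week intervention.

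**Working it through.** **Inputs.** N = 35, power 0.80, alpha 0.05, detectable d = 0.49 and target d above 0.55 come from Section 4.g; the enrolment ceiling of 45 is from Section 4.b.ii. Assumptions: d is in SD of the paired difference, tests are two-sided, there is no dropout, and correlations between time points are equal where contrasts are considered jointly.

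**1. The plan's own figure.** Paired t-test, noncentrality d x sqrt(N), df = 34. At d = 0.49: 0.49 x 5.916 = 2.90, power 0.804. The minimum detectable d is 0.487. The stated 0.49 reproduces.

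**2. Precision of week 8 vs week 4.** 95% CI half-width = t(0.975, 34) / sqrt(35) = 2.032 / 5.916 = 0.344 SD of change. An observed zero does not exclude a true further gain of 0.275, which is half of 0.55. It does exclude one of 0.49 or 0.55.

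**3. Non-significance of week 8 vs week 4 under a steady rise, N = 35.**

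| Rise per 4 weeks | Total by week 8 | Power | Non-significant |
|---|---|---|---|
| 0.245 | 0.49 | 0.291 | 71% |
| 0.275 | 0.55 | 0.353 | 65% |
| 0.40 | 0.80 | 0.633 | 37% |
| 0.49 | 0.98 | 0.804 | 20% |
| 0.55 | 1.10 | 0.885 | 12% |

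The balance point (50%) is a total of about 0.68. With 45 participants and a total of 0.55, non-significance is 56%. If the 0.55 total is instead in raw-score SD units, it is 65%, 47% or 30% at a within-person correlation of 0.5, 0.7 or 0.8.

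**4. The contrasts taken together** (20,000 simulated trials per shape, N = 35).

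- Straight line, 0.275 then 0.275: week 4 vs 0 is significant in 35% of trials and week 8 vs 0 in 89%. The full pattern (both significant, week 8 vs 4 not) appears in 28%. If the two increases need only be positive in sign, it appears in 64%.
- Among the 35% with a significant week 4 gain, week 8 vs 4 is non-significant in 82%. The shared week 4 score drives this: under equal correlations the two gains correlate at -0.5.
- If near zero means a point estimate within 0.10 or 0.20, the straight line meets it in 13% or 32% of trials.
- True step, 0.55 then 0: the full significant pattern appears in 78%.

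**5. The direct contrast.** (week 4 - week 0) - (week 8 - week 4) = 2 x week 4 - week 0 - week 8. Under equal correlations its variance is proportional to 4 + 1 + 1 = 6, against 1 + 1 = 2 for a paired difference, so its SD is sqrt(3) = 1.73 times as large.

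- Straight line: the true value is 0, and it falsely indicates an early peak in about 2.5% of trials.
- Full step of 0.55: 0.55 / 1.73 = 0.318; 0.318 x 5.916 = 1.88; power 0.447 (0.442 by simulation). About 80 participants would give 80%.
- CI half-width at N = 35: 0.344 x 1.73 = 0.60.

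**The case against.** The strongest reply is that the plan does not commit the error. It states an expectation and never says that a non-significant week 8 vs week 4 contrast will count as a plateau. Section 4.g disclaims significance as the aim, and Section 4.f says effect sizes will be calculated. H2 in Section 2 concerns increases relative to the pretest period, not timing. The planned contrasts read jointly do discriminate: 78% for a true step against 28% for a straight line. The early-minus-late difference can also be derived from the planned model.

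Most of this stands, and it limits the point. Four stronger readings are tempting but not supported:

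- A reader might infer that a steady rise would usually look like a plateau. That needs a total rise below about 0.68, a non-significance criterion, and week 4 vs 0 needing only a positive sign. The documents supply none of these.
- A reader might infer that a plateau conclusion is nearly assured whatever the true shape. The 28% and 64% figures contradict this.
- A reader might infer that the data could not exclude a late gain equal to the early one. That is so only if the early gain is below about 0.34, which is less than the study is powered to detect.
- A reader might infer that the result feeds directly into the follow-on efficacy trial. Section 10.B names only the comparator, not duration or response shape.

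What the reply does not remove is the mismatch. Section 4.f says the contrasts will test the pattern, and the one assigned to early change does not compare early with late. The effect sizes are promised for the intervention's impact on the mechanisms, not for the shape of response.

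**Conclusion.** The concern holds in limited form. The mismatch between hypothesis and contrast, and the absence of a criterion, follow from the text of Section 4.f and need no assumption. The limit on what a near-zero result can show follows from N = 35 alone.

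How often a steady rise would be left with a non-significant late contrast is conditional: about 65% for a total of 0.55 by week 8, but about 20% to 12% for 0.49 to 0.55 per 4 weeks. The documents do not say which timing is intended. These figures rest on no dropout and effects in SD of change; the joint results also assume equal correlations.

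Severity is minor: this is a secondary expectation in a pilot, and no go/no-go rule uses it.

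**What to change.** In Section 4.f, test the early-change hypothesis with 2 x week 4 - week 0 - week 8, estimated from the same multilevel model with its 95% CI. Keep week 8 vs week 4 as an estimate with its 95% CI, and state that a non-significant result is not evidence of a plateau.

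The cost is one contrast and one sentence, with no new data. The downside is low power, about 0.44 for a full 0.55 step, so the shape will often have to be reported as not determined.

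A formal plateau claim would need a margin set in advance, and N = 35 supports only a wide one. With a true difference of zero, an equivalence test has power of about 0.07 at a margin of 0.30 and 0.79 at 0.50. Estimation is therefore the realistic goal.
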